7.1.3. Study Duration

The study is event driven and total duration will be determined by the time required to accrue approximately 127 primary endpoint events, estimated to be approximately 10 years. Subjects are expected to have a minimum follow-up time of approximately 6 years.

7.2. Number of Subjects

It is expected that approximately 428 subjects will be randomized in the study to achieve 127 adjudicated primary endpoint events. In the event additional subjects are needed to complete enrollment in the biopsy substudy (N = 45 subjects, as defined in Addendum 2), subjects who agree to participate in the substudy may be added to the target subject enrollment number currently planned.

7.3. Planned Dosing Regimen

Subjects will be randomized to treatment with either OCA or matching placebo in a 1:1 ratio. Subjects will be dosed according to their cirrhosis status (as defined in [Section 9.7.3](#)) and applicable Child-Pugh Score (see [Section 9.7.4](#)) as outlined in [Table 3](#).

Subjects who are noncirrhotic or classified as Child-Pugh A at screening will receive 5 mg OCA or matching placebo once daily for 3 months. Subjects should titrate to a maximum dose of 10 mg OCA once daily (or matching placebo) at the Month 3 visit or at any study visit following the Month 3 visit based on tolerability of the product and assessment of biochemical response. Up-titration should be considered when ALP and/or total bilirubin are >ULN. A review of safety laboratory results (eg, chemistry, hematology, and coagulation) obtained no more than 2 months prior to the planned up-titration visit must be completed as part of the product tolerability assessment before up-titration can occur (see [Section 7.4.1](#)).

For those subjects that up-titrate to 10 mg, dose may be decreased to 5 mg at any time during the study as considered clinically appropriate (eg, tolerability). Subjects may be titrated back up to a maximum dose of 10 mg once daily based on tolerability and clinical judgment of the Investigator. A review of safety laboratory results obtained within 2 months of the planned up-titration visit date is not required prior to re-challenging a subject up to 10 mg once daily dosing, as long as the decrease in dose/dosing frequency was less than 3 months in duration.

Table 3: Planned Dosing Regimen by Cirrhosis and Child Pugh Score

	Scheduled Dosing Regimen		
	Standard	Modified ^a	
	Noncirrhotic/ Child-Pugh A	Child-Pugh B	Child-Pugh C
Starting Dose^b (Day 0)	5 mg daily	5 mg once weekly	5 mg once weekly
Titration 1^c (≥Month 3)	10 mg daily	5 mg twice weekly ^d	5 mg twice weekly ^d
Titration 2^c (≥6 weeks after Titration 1)	NA	10 mg twice weekly ^d	10 mg twice weekly ^d
Titration 3^c (≥6 weeks after Titration 2)	NA	5 mg daily	NA

^a Refer to [Appendix A](#) for additional instructions regarding subjects following the Modified Dosing Regimen.

^b Starting dose based on subject's cirrhosis status and Child-Pugh score at Screening.

^c Planned titration regimen is shown; however, the titration of dose and/or frequency is dependent on subject tolerability, biochemical response, and/or changes in cirrhosis status or Child-Pugh score at any time during the study (see Section 7.4).

^d Dosing per the twice weekly schedule must be at least 3 days apart.

The dosing regimen should be determined as described in Table 4. Investigators should follow the dosing/titration schedule as shown in Table 3.

Table 4: Determination of Dosing Regimen

Cirrhosis?	No	Yes	Yes	Yes
Child-Pugh Score	Any	A	B	C
Dosing Regimen	Standard		Modified for Child-Pugh B	Modified for Child-Pugh C

7.4. Dose Titration Criteria

Dose titration may follow the scheduled dosing regimens described in [Section 7.3](#) or occur due to tolerability concerns or as a result of changes in a subject's cirrhosis status (using histology or non-histological methods as defined in [Section 9.7.3](#) and [Section 9.7.4](#)) or Child-Pugh Score.

Dose titrations may involve increases or decreases in dosing frequency or dose and are dependent on tolerability (as assessed by a review of AEs and safety laboratory results) as well as biochemical response (as assessed by reductions in ALP and/or total bilirubin). In general, down-titration will be done in response to tolerability concerns and can occur at any time while on-study. Up-titration will be done per protocol when subjects have no tolerability concerns and have not achieved an adequate reduction in ALP and/or total bilirubin to within normal limits, or as assessed by the Investigator, or following resolution of a tolerability concern that previously led to down-titration. Up-titrations may only occur to the maximum dose and frequency for each dosing regimen as defined in Section 7.3.

Scheduled Dose Titration - The first dose titration for any subject may occur no earlier than 3 months following initiation of OCA or matching placebo. Subsequent titrations in dose or dosing frequency for subjects following the Modified Dosing Regimens may occur no earlier

than 6 weeks (via an unscheduled visit or regular visit- see [Appendix A](#)) following an up-titration.

Tolerability Dose Titration - Investigators may decrease the dosing frequency or dose for any subject at any time during the study, as considered clinically appropriate (eg, tolerability; see [Section 7.4.1](#)).

Dose Titration due to Change in Cirrhosis or Child-Pugh Score - When subjects demonstrate a change in cirrhosis status (as assessed per [Section 9.7.3](#)) or Child-Pugh Score ([Section 9.7.4](#)), dosing should be reassessed and the dosing regimen modified appropriately. Changes to the dosing regimen are not mandatory and should be based on clinical judgment as well as change in cirrhosis status. Table 5 provides an overview of the possible changes in dosing regimen due to changes in cirrhosis or Child-Pugh Score. Dosing should follow the titration schedule of the new dosing regimen such that the maximum dose within that dosing regimen is ultimately attained, based on tolerability, biochemical response, and clinical judgment.

Table 5: Changes in Dosing Regimen Due to Changes in Cirrhosis Status or Child-Pugh Score

Original Status	New Status ^a		
	Noncirrhotic OR Child-Pugh A	Child-Pugh B	Child-Pugh C
Noncirrhotic or Child-Pugh A	No Change	10 mg daily → 5 mg daily 5 mg daily → No change or 10 mg twice weekly ^b	5 mg or 10 mg daily → 10 mg twice weekly ^b
Child-Pugh B	5 mg daily → 10 mg daily	No Change	5 mg daily → 10 mg twice weekly ^b 10 mg twice weekly ^b → No change or 5 mg twice weekly 5 mg twice weekly ^b → No change or 5 mg once weekly
Child-Pugh C	10 mg twice weekly → 5 mg daily	10 mg twice weekly → 5 mg daily 5 mg twice weekly → No change or 10 mg twice weekly ^b 5 mg once weekly → 5 mg twice weekly	No Change

^a Once a subject begins dosing with the new dosing regimen, titration should occur as described for that dosing regimen in [Section 7.3](#) or Appendix A.

^b Dosing per the twice weekly schedule must be at least 3 days apart.

Subjects who exhibit development of cirrhosis at any point in the study should be assessed per [Section 9.7.3](#). If the presence of cirrhosis is confirmed and the subject's Child-Pugh score is either B or C, the appropriate modified dosing regimen should be followed. The dose or frequency of investigational product should be down-titrated to the next lowest dosing frequency in the appropriate modified dosing regimen unless the subject is currently taking a dose and frequency also specified in the modified dosing regimen and the Investigator determines that it is clinically appropriate for the subject to continue at that dose ([Appendix A](#)).

Subjects with pre-existing cirrhosis who demonstrate a change in the Child-Pugh Score from A to B or C at any point in the study should also have their dosing modified per the appropriate

dosing regimen. Changes in Child-Pugh Score that result from a transient, explainable change in laboratory parameters should be documented appropriately and should not necessarily result in a change to the dosing regimen ([Appendix A](#)).

Subjects who demonstrate an improvement in cirrhosis status or in Child-Pugh Score from B to A, or from Child-Pugh C to B, may be eligible to transition to the standard dosing regimen or the modified dosing for Child-Pugh B, respectively, based on tolerability. Prior to any dosing change, subjects must meet pre-titration assessment requirements for dosing as described in Section 7.4.1.

Child-Pugh Scores will be calculated at all quarterly study visits. All associated visit data (including central laboratory results) should be entered into the eCRF in a timely fashion to confirm that the subject's Child Pugh Score has not changed. If a change in cirrhosis status (as defined in [Section 9.7.3](#)) and/or Child-Pugh Score is observed independent of a study visit, the subject should be contacted via phone to discuss the need for a dosing modification and should be asked to return to the investigational site as soon as possible if a new bottle of investigational product is required to be dispensed.

Subjects' dose and dosing frequency may be titrated up or down within the appropriate dosing regimen based on the calculated Child-Pugh Scores. Up-titration should be done per Investigator discretion and be guided by the pre-titration tolerability assessments.

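### Section 7.4 and Appendix A leave dose reduction optional after worsening to Child-Pugh B or C, so no firm ceiling stops 10 mg daily from continuing

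*Protocol*

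**What the plan says.** Protocol section 7.4, under dose titration due to change in cirrhosis or Child-Pugh score, first says that "dosing should be reassessed and the dosing regimen modified appropriately". The next sentence reads: "Changes to the dosing regimen are not mandatory and should be based on clinical judgment as well as change in cirrhosis status". The section then introduces Table 5 as an overview of possible changes.

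After Table 5, the same section gives specific instructions:

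- New confirmed cirrhosis with class B or C: the subject is pointed to the modified regimen for that class, and a step down is described: "The dose or frequency of investigational product should be down-titrated to the next lowest dosing frequency in the appropriate modified dosing regimen". One exception is given, in two parts: what the subject now takes must already be a step of that modified regimen, and the Investigator must think it right to stay there.
- Pre-existing cirrhosis moving from A to B or C: subjects "should also have their dosing modified per the appropriate" regimen.
- Temporary laboratory shifts: "Changes in Child-Pugh Score that result from a transient, explainable change in laboratory parameters should be documented appropriately", and need not lead to a regimen change.

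Table 5 moves 10 mg daily to 5 mg daily on a change to B, and 5 or 10 mg daily to 10 mg twice weekly on a change to C. It lists staying put as an option for 5 mg daily moving to B, but not for 10 mg daily moving to B or C. In Tables 3 and 12 the modified regimens stop at 5 mg daily (B) and 10 mg twice weekly (C).

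The one sentence in 7.4 that makes a maximum binding concerns increases: "Up-titrations may only occur to the maximum dose and frequency for each dosing regimen as defined in Section 7.3".

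Appendix A repeats the optional clause. Its sentence opens with subjects already on a modified regimen, but its list of scenarios also covers newly developed cirrhosis with B or C, and pre-existing cirrhosis moving from A to B or C.

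**The concern.** The general clause covers a case that the specific text leaves without an exception: a cirrhotic subject on 10 mg daily whose class changes to B or C and stays there. If the general discretion governs, the two narrow exceptions add nothing. If the specific text governs, the general clause misleads. The protocol does not say which prevails.

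The situation is foreseeable, because hepatic worsening is what the trial measures. Section 5.5.2.2 says the lower doses in B and C are meant to give hepatic exposure similar to that of patients with normal function, and an unchanged 10 mg daily overshoots that aim. There is also a consistency problem. Two sites could treat the same kind of A-to-C subject at 70 or 20 mg/week and both claim compliance. It would then be unclear whether remaining on 10 mg daily is a violation relevant to the Per Protocol Population in section 13.1.1.

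**Working it through.** The plan states no figure on this point to reproduce. The check has three parts.

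**1. Weekly dose** (Tables 3, 5 and 12; dose × administrations per week)

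- 10 mg daily: 10 × 7 = 70 mg/week.
- Class B maximum, 5 mg daily: 5 × 7 = 35 mg/week. Ratio 70/35 = 2.0.
- Class C maximum, 10 mg twice weekly: 10 × 2 = 20 mg/week. Ratio 70/20 = 3.5.

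10 mg daily appears at no step of either modified regimen, so the exception for a dose already in the regimen cannot apply to it.

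**2. Predicted liver exposure** (section 5.5.2.2 model factors: 1.5 for B, 1.7 for C)

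Exposure is taken as weekly dose × factor. The reference is normal hepatic function on 10 mg daily, 70 × 1 = 70.

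| Situation | Dose × factor | Relative to 70 |
|---|---|---|
| B, unchanged 10 mg daily | 70 × 1.5 = 105 | 1.5 |
| C, unchanged 10 mg daily | 70 × 1.7 = 119 | 1.7 |
| B at class maximum | 35 × 1.5 = 52.5 | 0.75 |
| C at class maximum | 20 × 1.7 = 34 | 0.49 |
| C, 5 mg daily kept after B to C | 35 × 1.7 = 59.5 | 0.85 |

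The last row is the path that the opening words of Appendix A most directly leave open. It exceeds the C maximum by 59.5/34 = 1.75, but stays below the reference exposure.

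**3. Do other rules force a reduction?** (Table 6; sections 8.4.1.1 and 8.4.1.2)

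These values are illustrative assumptions: cirrhosis present, baseline bilirubin 1.8 mg/dL, baseline score 5, stable ALT and AST.

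- A to B: bilirubin 2.2 (2 points), albumin 3.4 g/dL (2), other three factors 1 each. Total 7, class B. Bilirubin ratio 2.2/1.8 = 1.22, below both the 1.5× threshold for repeat testing and the 2× threshold for interruption.
- A to C: bilirubin 3.2 (3), albumin 2.7 (3), mild ascites (2), INR (1), encephalopathy (1). Total 10, class C. Ratio 3.2/1.8 = 1.78, which triggers repeat testing but not mandatory interruption.

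A class change can therefore occur without reaching the mandatory interruption rule.

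**The case against.** The best reply is that this is a recommendation with discretion, stated deliberately in two places. Most of the opposing text says *should*, and Table 5 lists possible changes. The optional clause is itself guided by clinical judgment and change in cirrhosis status. Read specific over general, a lasting 10 mg daily in B or C departs from the later paragraphs of 7.4. All of that stands, so two stronger readings fail. A reader might infer that the clause is wholly unrestricted, or that the protocol plainly licenses 10 mg daily; the documents support only that nothing firmly prevents it.

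A reader might also infer a conflict with section 9.7.3.1. There is none: that section sets the regimen from the Screening assessment and, for later changes, asks only for re-evaluation, which agrees with 7.4.

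Safeguards exist. Section 7.4 provides quarterly scoring and telephone contact about dosing when a change is seen between visits. Section 8.4 continues product after an outcome event only if no interruption criterion is met and the Investigator judges it safe. Section 8.4.1.2 requires interruption for symptoms of hepatotoxicity with enzyme elevations, discontinuation for suspected related severe injury, and Medical Monitor contact for persistent elevations. These lower the risk, but none caps a continued dose.

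The harm evidence is modest. Section 5.5.2.2 calls the rise in liver exposure modest and reports no apparent safety impact in earlier B and C subjects. Section 5.6 reports more hepatobiliary findings at 10 to 50 mg daily, but not by Child-Pugh class, and that range includes this trial's standard 10 mg dose. The class maxima also undershoot the similar-exposure aim. This limits the weight of the point without removing the ambiguity.

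**Conclusion.** The point holds as an ambiguity with a safety and consistency consequence. Sections 7.4 and Appendix A make regimen change optional, the narrower text is advisory, and the maximum binds only increases. A cirrhotic subject with a lasting change to B or C can remain on 10 mg daily on a fair reading. Noncirrhotic subjects are not affected, because Table 4 keeps them on the standard regimen at any score.

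The excess over the class maximum is 2.0-fold in B and 3.5-fold in C by weekly dose. A reader might take those ratios, or the larger plasma factors in section 5.5.2.2, as the overexposure. They are not: against the protocol's own aim of similar hepatic exposure, the predicted overshoot is about 1.5 (B) to 1.7 (C). This rests on the model's liver factors holding at 10 mg daily; the comparisons with the class maxima also need exposure proportional to dose. Keeping 5 mg daily after B to C breaks the class maximum but does not overshoot the exposure aim.

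Given the existing monitoring and the modest harm evidence, this is a cheap improvement worth making, not a flaw that threatens the trial's conclusions.

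**What to change.** In section 7.4 and in Appendix A, limit the optional wording to two situations: the dose is at or below the maximum for the new class, or the score change is transient, explainable and documented as such. Outside those, require that when a subject with cirrhosis, new or pre-existing, worsens to B or C, the dose is reduced at least to that class's maximum (5 mg once daily for B, 10 mg twice weekly for C). State in 7.4 that the class maximum applies to any continued dose as well as to up-titrations. Table 5 can stay as it is, and its options to remain on the current dose still apply at or below the maximum.

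The cost is a wording change in two places, with matching guidance to sites and in the IWRS. Investigators lose some discretion above maxima the protocol already sets, and placebo subjects undergo matching blinded reductions. No visits, tests or subjects are added.

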7.4.1. Pre-Titration Tolerability Assessment Requirements

Tolerability of investigational product must be assessed prior to titrating a subject to a higher dose. A review of adverse events and safety laboratory results (eg, chemistry, hematology, and coagulation) obtained within 2 months of the up-titration visit must be performed as part of the investigational product tolerability assessment, prior to any planned up-titration in study medication (eg, Month 3, Month 6). Safety laboratory results obtained at the Month 1 visit (for titration at Month 3) or at the 1 Month Post-Titration Assessment visit (for titration prior to or at the subsequent quarterly visit) are acceptable for review purposes; however, if for any reason, laboratory results are not available at the time of the planned up-titration visit, additional laboratory samples must be obtained and reviewed, prior to up-titrating the subject to a higher dose.

To be eligible for a dose up-titration:

- Subjects should not be experiencing significant AEs that are suspected to be related to investigational product (eg, severe pruritus) or displaying other symptoms that may indicate intolerability of investigational product.
- There must be no clinically significant increase (as determined by the Investigator) in the subject's liver function tests.

7.5. Criteria for Study Termination

The Sponsor reserves the right to terminate the study at any time. It is normal procedure to review the emerging clinical and safety data. As a result of such a review or a recommendation by the DMC, it may be necessary to stop the study before all events have been accrued, and when subjects are still active on the study. In addition, the Sponsor may terminate the study at

an investigational site at any time (eg, poorly performing sites, as determined by the number of subjects enrolled or the quality of the study data).

The Investigator and/or Sponsor (or designee) must notify the Institutional Review Board/Independent Ethics Committee (IRB/IEC) of discontinuation of a site or the study and the reason for doing so.

Investigators will be informed by the Sponsor as to when the final study visit is to be completed, and should then schedule all subjects for the End of Study Visit. The window of time for scheduling the visit will be based on a final projection of when the requisite 127 adjudicated events will have been accrued.

8. SELECTION AND WITHDRAWAL OF SUBJECTS

8.1. Subject Population

This study will be conducted at approximately 170 international study sites with experience in treating patients with PBC. Prospective subjects will be identified primarily from the hospital and/or physician's database of patients with PBC, or may be referred from other physicians. Patients may self-refer to an Investigator if they become aware of the study through local, national, or international PBC patient societies, forums, or networks.

8.2. Subject Inclusion Criteria

1. Definite or probable PBC diagnosis (consistent with AASLD and EASL practice guidelines; [Lindor 2009](#); [EASL 2009](#)), as demonstrated by the presence of ≥ 2 of the following 3 diagnostic factors:
 - History of elevated ALP levels for at least 6 months.
 - Positive antimitochondrial antibody (AMA) titer or if AMA negative or in low titer ($<1:80$) PBC-specific antibodies (anti-GP210 and/or anti-SP100 and/or antibodies against the major M2 components [PDC-E2, 2-oxo-glutaric acid dehydrogenase complex]).
 - Liver biopsy consistent with PBC.
2. A mean total bilirubin $>ULN$ and $\leq 5x ULN$ and/or a mean ALP $>3x ULN$
3. Age ≥ 18 years
4. Either is not taking UDCA (no UDCA dose in the past 3 months) or has been taking UDCA for at least 12 months with a stable dose for ≥ 3 months prior to Day 0.
5. Contraception: Female subjects of child-bearing potential must use ≥ 1 effective method of contraception during the study and until 30 days following the last dose of investigational product. Effective methods of contraception are considered to be those listed below:
 - Barrier method, ie, (a) condom (male or female) or (b) diaphragm, with spermicide
 - Intrauterine device (IUD)

- Vasectomy (partner)
 - Hormonal (eg, contraceptive pill, patch, intramuscular implant or injection)
 - Abstinence, if in line with the preferred and usual lifestyle of the subject
6. Must provide written informed consent and agree to comply with the study protocol

8.3. Subject Exclusion Criteria

1. History or presence of other concomitant liver diseases including:
 - Hepatitis C virus infection
 - Active hepatitis B infection; however, subjects who have seroconverted (hepatitis B surface antigen and hepatitis B e antigen negative) may be included in this study after consultation with the Medical Monitor.
 - Primary sclerosing cholangitis
 - Alcoholic liver disease
 - Definite autoimmune liver disease or overlap hepatitis
 - Nonalcoholic steatohepatitis
 - Gilbert's Syndrome
2. Presence of clinical complications of PBC or clinically significant hepatic decompensation, including:
 - History of liver transplant, current placement on a liver transplant list, or current MELD score >12. Subjects who are placed on a transplant list despite a relatively early disease stage (for example per regional guidelines) may be eligible as long as they do not meet any of the other exclusion criteria.
 - Cirrhosis with complications, including history (within the past 12 months) or presence of:
 - Variceal bleed
 - Uncontrolled ascites
 - Encephalopathy
 - Spontaneous bacterial peritonitis
 - Known or suspected hepatocellular carcinoma
 - Prior transjugular intrahepatic portosystemic shunt procedure
 - Hepatorenal syndrome (type I or II) or Screening (visit 1 or 2) serum creatinine >2 mg/dL (178 µmol/L)
3. Mean total bilirubin >5x ULN
4. Subjects who have undergone gastric bypass procedures (gastric lap band is acceptable) or ileal resection or plan to undergo either of these procedures.

5. Other medical conditions that may diminish life expectancy, including known cancers (except carcinomas *in situ* or other stable, relatively benign conditions such as chronic lymphatic leukemia).
6. If female: plans to become pregnant, known pregnancy or a positive urine pregnancy test (confirmed by a positive serum pregnancy test by the central laboratory), or lactating.
7. Known history of human immunodeficiency virus infection.
8. Medical conditions that may cause non-hepatic increases in ALP (eg, Paget's disease or fractures within 3 months).
9. Other clinically significant medical conditions that are not well controlled or for which medication needs are anticipated to change during the study.
10. History of alcohol abuse or other substance abuse within 1 year prior to Day 0.
11. Participation in another investigational product, biologic, or medical device study within 30 days prior to Screening. Participation in a previous study of OCA is allowed with 3 months washout prior to enrollment in this study.
12. Mental instability or incompetence, such that the validity of informed consent or ability to be compliant with the study is uncertain.
13. History of known or suspected clinically significant hypersensitivity to OCA or any of its components.
14. UDCA naïve (unless contraindicated)

